5.3 Concomitant Medications

5.3.1 Allowed Concomitant Medications

All treatments the investigator considers necessary for a subject's welfare may be administered at the discretion of the investigator in keeping with the community standards of medical care. Transfusion of blood products and administration of myeloid growth factors may be considered for chemotherapy-induced myelosuppression including anemia, thrombocytopenia, and neutropenia as indicated by signs and symptoms, laboratory results, and as determined by the investigator.

All concomitant medications received within 28 days before the first dose of study drug through 30 days after the last dose of study drug should be recorded in the EDC. Concomitant medications administered more than 30 days after the last dose of trial treatment should be recorded only if associated with a serious adverse event (SAE) as defined in Section 11.1.2 and if the SAE meets the reporting criteria in Section 11.2.2.

Medications administered during a procedure (anesthetics, etc.) will not be collected as concomitant medications. However, the procedure itself should be recorded on the adverse event page of the EDC.

5.3.2 Prohibited Concomitant Medications

Strong CYP3A4 inducers

Patients receiving concomitant non-liposomal irinotecan and CYP3A4 enzyme-inducing anticonvulsants including phenytoin, phenobarbital or carbamazepine have substantially reduced exposure to irinotecan (AUC reduction by 12% with St John's wort, 57%-79% with phenytoin, phenobarbital, or carbamazepine) and SN-38 (AUC reduction by 42% with St John's wort, 36%-92% with phenytoin phenobarbital, or carbamazepine). Therefore, co-administration of irinotecan liposome injection with inducers of CYP3A4 may reduce systemic exposure of irinotecan liposome injection.

Strong CYP3A4 inhibitors and UGT1A1 inhibitors

Patients receiving concomitant non-liposomal irinotecan and ketoconazole, a CYP3A4 and UGT1A1 inhibitor, have increased SN-38 exposure by 109%. Therefore, co-administration of irinotecan liposome injection with other inhibitors of CYP3A4 (e.g. grapefruit juice, clarithromycin, indinavir, itraconazole, lopinavir, nefazodone, nelfinavir, ritonavir, saquinavir, telaprevir, voriconazole) may increase systemic exposure of irinotecan liposome injection. Based on the drug interaction of non-liposomal irinotecan and ketoconazole, co-administration of irinotecan liposome injection with other inhibitors of UGT1A1 (e.g. atazanavir, gemfibrozil, indinavir) may also increase systemic exposure of irinotecan liposome injection.

The prohibited medications are listed in Table 1 in the protocol appendix.

5.4 Supportive Care

Drugs-associated toxicities may require symptomatic management and may be administered at the discretion of the investigator in keeping with the community standards of medical care. For example, irinotecan liposome injection can cause life-threatening myelosuppression, neutropenia, and diarrhea. The complications of neutropenia such as neutropenic fever and neutropenic sepsis should be managed promptly with antibiotics; granulocyte-colony stimulating factor (G-CSF) may be used to manage neutropenia at the investigator's discretion. Early-onset diarrhea (occurring during or shortly after infusion of irinotecan) may be prevented by pre-medication with atropine prior to administration of irinotecan liposome injection. Late diarrhea (generally occurring more than 24 hours after administration of irinotecan) should be treated promptly with loperamide, fluid and electrolyte replacement for dehydration, and antibiotics if ileus, fever, or severe neutropenia develops. In case of severe hypersensitivity reactions, acute infusion reactions (rash, urticarial, periorbital edema, pruritis), or interstitial lung disease (dyspnea, cough, fever), irinotecan liposome injection should be discontinued, and the symptoms should be managed according to existing standard guidelines.

5.5 **Reproductive Information**

Participants of childbearing potential who are sexually active and their partners must agree to abstain from behaviors that could lead to pregnancy (heterosexual activity, sperm donation, in vitro fertilization, etc.) or to use 2 forms of effective methods of contraception beginning with time of consent, during the study treatment and for 9 months (females) or 6 months (males) after last dose of study treatment(s). Two contraception methods can be comprised of two barrier methods, or a barrier method plus a hormonal method. See below for options of acceptable non-hormonal birth control methods:

• Total sexual abstinence i.e., refrain from any form of sexual intercourse in line with the patients' usual and/or preferred lifestyle. Abstinence must be for the total duration of the

study treatment and for at least 9 months (females) or 6 months (males) after the last dose of study treatment. Periodic abstinence (e.g., calendar ovulation, symptothermal, post-ovulation methods) and withdrawal are not acceptable methods of contraception.

- Vasectomised sexual partner PLUS male condom. With participant assurance that partner received post-vasectomy confirmation of azoospermia.
- Tubal occlusion PLUS male condom
- Intrauterine Device PLUS male condom. Provided coils are copper-banded.

Acceptable hormonal methods:

- Etonogestrel implants (eg, Implanon[®], Norplant[®]) PLUS male condom
- Normal and low dose combined oral pills PLUS male condom
- Hormonal shot or injection (eg, Depo-Provera) PLUS male condom
- Intrauterine system device (eg, levonorgestrel-releasing intrauterine system Mirena[®]) PLUS male condom

6. TOXICITIES AND DOSE DELAYS/DOSE MODIFICATIONS

The NCI Common Terminology Criteria for Adverse Events (CTCAE) Version 5 will be used to grade adverse events. Subjects enrolled in this study will be evaluated clinically and with standard laboratory tests before and at regular intervals during their participation in this study as specified in Study Calendar & Evaluations. Subjects will be evaluated for adverse events (all grades), serious adverse events, and adverse events requiring study drug interruption or discontinuation as specified in Study Calendar & Evaluations.

6.1 Dose Delays/Dose Modifications

Unless otherwise noted in the dose modification tables below, treatment may be delayed up to 28 days from the expected day of the next treatment for any reason. If treatment is delayed ≤ 28 days, subjects will proceed with the next cycle of treatment at the dose level recommended according to the tables below. Any dosing interruption will not increase the duration of the cycle or treatment. Held or missed doses will not be made up.

If a treating investigator determines a dose reduction is in a subject's best interest, yet the subject fails to meet the guidelines below, the dose reduction must be discussed with the sponsor investigator on a case-by-case basis. Please contact the Big Ten CRC project manager to arrange this discussion.

6.2 Dose Levels for Dose Reductions

If dose level below that outlined in the table is required, subject will be removed from protocol mandated treatment and followed-up per protocol.

Dose level	Dose of Irinotecan liposome injection (free base)	Dose of Oxaliplatin	Dose of 5- Fluorouracil
Starting Dose	50 mg/m^2	60 mg/m^2	$2,400 \text{ mg/m}^2$
Dose level (-1)	40 mg/m ²	48 mg/m^2	1,920 mg/m ²

Dose level (-2)	30 mg/m ²	36 mg/m^2	1,440 mg/m ²
-----------------	----------------------	---------------------	-------------------------

6.2.1 Dose Reduction of nal-IRI

- a. If the subject develops grade 3 or 4 diarrhea, nal-IRI will be withheld until diarrhea resolves to ≤ grade 1. Loperamide will be initiated for late onset diarrhea of any severity. Intravenous or subcutaneous atropine 0.25 mg to 1 mg will be administered (unless clinically contraindicated) for early onset diarrhea of any severity. Upon recovery to Grade 1, resume nal-IRI at 40 mg/m² for first occurrence or 30 mg/m² for second occurrence; discontinue nal-IRI for third occurrence.
- b. If the subject develops interstitial lung disease or anaphylactic reaction, nal-IRI will be discontinued at first occurrence.

6.2.2 Dose Reduction of Oxaliplatin

- a. If the subject develops persistent grade 2 neurosensory events, the dose of oxaliplatin will be reduced to 48 mg/m^2 for first occurrence, or 36 mg/m^2 for second occurrence.
- b. If the subject develops grade 3 or 4 gastrointestinal toxicities (despite prophylactic treatment) and recovers from them, the dose of oxaliplatin will be reduced to 48 mg/m² for first occurrence, or 36 mg/m² for second occurrence.
- c. If the subject develops grade 4 neutropenia or febrile neutropenia or grade 3/4 thrombocytopenia, the next dose will be delayed until neutrophils 1,500/µL and platelets 75,000//µL. Granulocyte colony-stimulating factor (G-CSF) may be administered as indicated.
- d. If the subject develops persistent grade 3 neurosensory events, discontinue oxaliplatin.

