1.3.3.1.1 Safety Data from Ongoing MM-398-07-02-03 Study

A Randomized, Open-label Phase 2 Study of Nanoliposomal Irinotecan (nal-IRI)-containing Regimens versus nab-paclitaxel plus Gemcitabine in Patients with Previously Untreated, Metastatic Pancreatic Adenocarcinoma (NCT02551991)

This study is an open-label, phase II study to assess the safety, dose-limiting toxicities (Part 1A only), tolerability, and preliminary efficacy of irinotecan liposome injection in combination with oxaliplatin+5-FU/LV in subjects with metastatic pancreatic adenocarcinoma who have not received prior systemic anti-tumor therapy. The study comprises an initial dose exploration (Part 1A) followed by dose expansion (Part 1B ongoing in the extension phase) of the irinotecan liposome injection+ oxaliplatin+5-FU/LV regimen.

For the 56 subjects treated, all (100.0%) had treatment-emergent adverse events (TEAEs). There were nine TEAEs that were defined as Dose Limiting Toxicities (DLTs) that were reported by five subjects across the four dose exploration cohorts (diarrhea, n=2; vomiting, anal fissure, anal inflammation, proctalgia, neutropenic infection, neutropenic sepsis, and febrile neutropenia, all n=1), including one subject treated in Part 1A- Cohort B who was included in the pooled analysis (febrile neutropenia)

Treatment-related TEAEs Grade 3 or higher were reported by 41 of 56 subjects, including 22 subjects from the pooled analysis of 32 subjects treated with irinotecan liposome injection 50 mg/m2+LV 400 mg/m2+5-FU 2400 mg/m2 and oxaliplatin 60 mg/m2. The TEAEs included: neutropenia, n=10; febrile neutropenia, hypokalemia, both n=4; diarrhea, nausea, both n=3; anemia, vomiting, both n=2, with no reported Grade 3 or higher fatigue or peripheral neuropathy.

SAEs were reported by 34 of the 56 treated subjects, including 17 of the 32 subjects in the pooled analysis, with 23 subjects reporting treatment-related SAEs. In the pooled analysis, 10 of the 32 subjects had treatment-related SAEs: nausea, febrile neutropenia, both n=3; diarrhea, vomiting, both n=2; colitis, enterocolitis, stomatitis, anemia, pneumonia, and pyrexia, all n=1. At the data cut-off there were no treatment-related TEAEs leading to death.

There were 19 subjects who reported TEAEs leading to discontinuation (including eight subjects in the pooled analysis), with 39 subjects requiring dose adjustment due to AEs (including 26 subjects in the pooled analysis).

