6.2.3 Dose Reduction of 5-Fluorouracil

- a. 5-fluorouracil will be held for any of the following:
 - Grade 3 or 4 diarrhea
 - Grade 2 or 3 palmar-plantar erythrodysesthesia (hand-foot syndrome)
 - Grade 3 or 4 mucositis
 - Grade 4 myelosuppression
- b. Upon resolution or improvement to Grade 1 diarrhea, mucositis, myelosuppression, or palmar-plantar erythrodysesthesia, resume administration of 5-fluorouracil at 1,920 mg/m² for first occurrence, or 1,440 mg/m² for second occurrence.
- c. 5-fluorouracil will be discontinued following development of any of the following adverse reactions:
 - Angina, myocardial infarction/ischemia, arrhythmia, or heart failure in patients with no history of coronary artery disease or myocardial dysfunction
 - Hyperammonemic encephalopathy
 - Acute cerebellar syndrome, confusion, disorientation, ataxia, or visual disturbance

6.3 **Protocol Therapy Discontinuation**

In addition to discontinuation from therapy related to toxicities as outlined above, a subject will also be discontinued from protocol therapy and followed up per protocol under the circumstances outlined below. The reason for discontinuation of protocol therapy will be documented on the electronic case report form (eCRF).

• Documented disease progression

- The treating physician thinks a change of therapy would be in the best interest of the subject
- The subject requests to discontinue protocol therapy, whether due to unacceptable toxicity or for other reasons
 - If a subject decides to prematurely discontinue protocol therapy ("refuses treatment"), the subject should be asked if he or she may still be contacted for further scheduled study assessments. The outcome of that discussion should be documented in both the medical records and in the eCRF.
- A female subject becomes pregnant
- If protocol therapy is interrupted for ≥ 28 days.

6.4 **Protocol Discontinuation**

If a subject decides to withdraw from the study (and not just from protocol therapy) all efforts should be made to complete the final study assessments. The site study team should contact the subject (ex. telephone, telehealth, clinic visit, etc.) to determine the reason for the study withdrawal. If the reason for withdrawal is an adverse event, it will be recorded on the eCRF.

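### nal-IRI has no myelosuppression rule of its own, and the oxaliplatin and 5-FU rules for the same treatment day differ in trigger and action

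*Combined protocol and SAP*

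**What the plan says.** Section 5.2 gives oxaliplatin, nal-IRI, leucovorin and 5-FU in sequence on Day 1 of each 14-day cycle. Section 6.2 then treats dose changes drug by drug.

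- **nal-IRI (6.2.1).** The only hold-and-reduce trigger is diarrhea: "If the subject develops grade 3 or 4 diarrhea, nal-IRI will be withheld until diarrhea resolves to ≤ grade 1". The drug is stopped at a third occurrence of diarrhea, or for interstitial lung disease or an anaphylactic reaction. No blood-count event is listed.
- **Oxaliplatin (6.2.2, item c).** Trigger and action stand in one sentence: "If the subject develops grade 4 neutropenia or febrile neutropenia or grade 3/4 thrombocytopenia, the next dose will be delayed until neutrophils 1,500/µL and platelets" reach 75,000/µL, with G-CSF allowed. No dose level is given. Items a, b and d name oxaliplatin; item c does not.
- **5-FU (6.2.3).** The blood-count trigger is "Grade 4 myelosuppression". On improvement to Grade 1 the drug resumes at the first reduced level, or at the second reduced level after a second occurrence. Febrile neutropenia and Grade 3 thrombocytopenia are not listed.

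Section 5.4 says that "irinotecan liposome injection can cause life-threatening myelosuppression, neutropenia, and diarrhea". For neutropenia it offers supportive care only (antibiotics, G-CSF). Section 6.1 lets treatment be delayed up to 28 days for any reason, after which "subjects will proceed with the next cycle of treatment at the dose level recommended according to the tables below". A reduction outside the guidelines must be discussed case by case with the sponsor investigator.

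**The concern.** Of the serious nal-IRI risks that Section 5.4 names, only diarrhea has a dose rule for nal-IRI. For blood-count toxicity there are two written rules that do not match, and a gap where the rule for the investigational drug would be. Nothing says how the drugs move together when one of them is delayed.

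This is first a patient-safety matter, because the gap concerns a toxicity that the protocol itself calls life-threatening. It also bears on what the trial can report. Tolerability is part of the hypothesis in Section 1.4, and Grade 3 and 4 toxicity is a secondary endpoint. If sites fill the gap differently, nal-IRI exposure after the same event will differ by site, and the tolerability summary will mix several practices.

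**Working it through.** The plan states no figure on this point to reproduce. The check sets the rules side by side, follows both readings of 6.2.2 item c, and then asks how often the gap would be met.

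**Rules by event**

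| Event | nal-IRI (6.2.1) | Oxaliplatin (6.2.2 c) | 5-FU (6.2.3) |
|---|---|---|---|
| Grade 4 neutropenia | none | delay to stated counts; no level assigned | hold; resume reduced |
| Febrile neutropenia, count not Grade 4 | none | delay to stated counts; no level assigned | none |
| Grade 3 thrombocytopenia | none | delay to stated counts; no level assigned | none |
| Grade 4 thrombocytopenia | none | delay to stated counts; no level assigned | hold; resume reduced |
| Day 1 neutrophils below 1,500/µL, not Grade 4, no prior item c event | none | none | none |

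**Reading 1: item c means oxaliplatin only.** After febrile neutropenia oxaliplatin waits for the counts. nal-IRI remains due, and so does 5-FU when the count is not Grade 4.

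**Reading 2: item c means the whole cycle.** The timing conflict goes away. After Grade 4 neutropenia 5-FU still resumes reduced, while no passage assigns a level to nal-IRI or oxaliplatin.

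**Section 6.1.** The delay is optional. The dose level to which it sends the reader is one that no blood-count trigger assigns for nal-IRI or oxaliplatin. The case-by-case clause makes a nal-IRI reduction after such an event an exception to the guidelines.

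**How often it would arise.** Section 1.3.3.1.1 reports treatment-related Grade 3 or higher events: "The TEAEs included: neutropenia, n=10; febrile neutropenia, hypokalemia, both n=4; diarrhea, nausea, both n=3". The natural denominator is the pooled 32 subjects at these doses, but the preceding sentence also mentions 56. The target sample size is 28 (Section 12.3).

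- Rate with 32: 4/32 = 12.5%. Exact (Clopper-Pearson) 95% limits: Beta(4, 29) at 0.025 = 3.5%; Beta(5, 28) at 0.975 = 29.0%.
- Expected in 28: 28 × 0.125 = 3.5 (28 × 0.035 = 1.0 to 28 × 0.290 = 8.1).
- P(at least one in 28) = 1 − (1 − 0.125)^28 = 0.976. At the lower limit: 1 − 0.965^28 = 0.63.
- With 56 as denominator: 4/56 = 7.1%; expected 28 × 0.0714 = 2.0; P = 1 − (52/56)^28 = 0.874.
- A cross-check without the denominator question: the same section gives febrile neutropenia as a treatment-related serious event in 3 subjects of the pooled 32. Then 3/32 = 9.4%; expected 28 × 3/32 = 2.6; P = 1 − (29/32)^28 = 0.94.

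The 10 neutropenia cases (10/32 = 31%, or 10/56 = 18%) show that the toxicity is common. They do not size the conflict between the two written rules. Both rules start at Grade 4 neutropenia, and the section does not separate Grade 3 from Grade 4.

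**The case against.** The strongest reply is that nal-IRI is not left without any means of being held or reduced, though a reader might infer that from Section 6.2.1 alone. Section 6.1 allows treatment to be delayed for any reason, which includes nal-IRI, and it allows a discussed reduction. Because item c names no drug and all the drugs are given on Day 1, a whole-cycle delay is a fair reading, and on it nal-IRI does have a mandatory hold after febrile neutropenia or Grade 4 neutropenia. This stands. What is missing is a mandatory rule that is clearly nal-IRI's own, together with any assigned level on resumption.

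Other stronger inferences also go beyond the text:

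- There are not three conflicting rules, but two differing rules and one gap.
- Reduced levels for nal-IRI and oxaliplatin do exist, in the Section 6.2 table. No blood-count event leads to them.
- The protocol does not order treatment at a low Day 1 count. It is silent, and 6.1 permits waiting.
- Different resumption levels for different drugs are not in themselves a contradiction. The fault is that for two of the drugs nothing is said.
- An effect on the 24-week disease control rate is not shown. That endpoint is RECIST status, not persistence on treatment.

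The objection narrows the point but does not remove it. Permission to delay is not an instruction, and each reading of item c leaves a gap.

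**Conclusion.** The point holds in this form: Section 6.2.1 gives nal-IRI no mandatory, drug-specific rule for neutropenia, febrile neutropenia or thrombocytopenia; the oxaliplatin and 5-FU rules differ in trigger and in action; the scope of 6.2.2 item c is unclear; and otherwise only the permissive text of 6.1 applies. The textual part needs no assumption.

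The size does. If rates resemble those of the metastatic cohort in Section 1.3.3.1.1, two to four febrile neutropenia cases are the plausible centre for 28 subjects, and at least one is likely on either denominator. The probability of 0.98 treats 12.5% as known; 0.63 at the lower limit is the more cautious figure. The trial should expect to meet the gap, but the documents do not show how many subjects would be handled differently because of it.

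**What to change.** Amend Section 6 so that 5.4, 6.1, 6.2.1, 6.2.2 item c and 6.2.3 agree:

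1. Give each blood-count event one consistent instruction that covers nal-IRI, oxaliplatin and 5-FU, preferably in a single table. Where a drug is meant to continue unchanged, say so.
2. State which drugs the delay in 6.2.2 item c covers.
3. State whether any count requirement applies on Day 1 when no item c event has occurred.

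The clinical content of each instruction is for the sponsor-investigator to set; none is proposed here.

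The cost is one protocol amendment. No new data are needed, since the study calendar already schedules a complete blood count with the treatment visits. Depending on what is decided, some doses that would now be given may be delayed.

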6.2.3 Dose Reduction of 5-Fluorouracil

- a. 5-fluorouracil will be held for any of the following:
 - Grade 3 or 4 diarrhea
 - Grade 2 or 3 palmar-plantar erythrodysesthesia (hand-foot syndrome)
 - Grade 3 or 4 mucositis
 - Grade 4 myelosuppression
- b. Upon resolution or improvement to Grade 1 diarrhea, mucositis, myelosuppression, or palmar-plantar erythrodysesthesia, resume administration of 5-fluorouracil at 1,920 mg/m² for first occurrence, or 1,440 mg/m² for second occurrence.
- c. 5-fluorouracil will be discontinued following development of any of the following adverse reactions:
 - Angina, myocardial infarction/ischemia, arrhythmia, or heart failure in patients with no history of coronary artery disease or myocardial dysfunction
 - Hyperammonemic encephalopathy
 - Acute cerebellar syndrome, confusion, disorientation, ataxia, or visual disturbance

6.3 **Protocol Therapy Discontinuation**

In addition to discontinuation from therapy related to toxicities as outlined above, a subject will also be discontinued from protocol therapy and followed up per protocol under the circumstances outlined below. The reason for discontinuation of protocol therapy will be documented on the electronic case report form (eCRF).

• Documented disease progression

- The treating physician thinks a change of therapy would be in the best interest of the subject
- The subject requests to discontinue protocol therapy, whether due to unacceptable toxicity or for other reasons
 - If a subject decides to prematurely discontinue protocol therapy ("refuses treatment"), the subject should be asked if he or she may still be contacted for further scheduled study assessments. The outcome of that discussion should be documented in both the medical records and in the eCRF.
- A female subject becomes pregnant
- If protocol therapy is interrupted for ≥ 28 days.

6.4 **Protocol Discontinuation**

If a subject decides to withdraw from the study (and not just from protocol therapy) all efforts should be made to complete the final study assessments. The site study team should contact the subject (ex. telephone, telehealth, clinic visit, etc.) to determine the reason for the study withdrawal. If the reason for withdrawal is an adverse event, it will be recorded on the eCRF.

